## 8.3.1.2. Symptom-Directed Physical Examination

A symptom-directed PE is to be performed on Days 8 and 15 of Cycle 1 by a qualified licensed individual. This will consist of a focused review of systems and physical examination addressing any new symptoms, AEs, or complaints.

These assessments will be completed as indicated in the Schedule of Assessments (Table 1).

#### **8.3.1.3.** Vital Sign Measurements

Blood pressure (BP), heart rate (HR), temperature (T) and respiratory rate (RR) must be measured after the subject has been sitting for five minutes.

#### **8.3.1.4.** ECOG Performance Status

Subject's performance status will be assessed using the ECOG performance status tool.

#### 8.3.2 Clinical Laboratory Assessments

All clinical laboratory assessments (per Table 4, which follows) will be performed at local laboratories according to the laboratory's normal procedures. Reference ranges will be supplied by the laboratory and used to assess the laboratory data for out of range pathological changes and CTCAE grades, where applicable.

**Table 4: Clinical Laboratory Panels** 

Hemate	ology a	Serum Chemistry	C	oagulation

 
WB (inc base)
 
hen
 
hen
 
plat
 
mea
 
(M0
 
mea
 
	blood cell count BC with differential cluding neutrophils, ophils, eosinophils, aphocytes, monocytes) noglobin natocrit telet count an corpuscular volume CV) an corpuscular hemoglobin CH) an corpuscular hemoglobin acentration (MCHC)	
 
albumin
 
amylase
 
alkaline phosphatase
 
ALT
 
AST
 
bicarbonate
 
BUN
 
calcium
 
chloride
 
creatinine
 
phosphorous
 
potassium
 
random glucose
 
sodium
 
total bilirubin
 
conjugated (direct) bilirubin (where possible)
 
total protein
 
magnesium
 
triglycerides
 
	•	PT PTT

ALT = alanine aminotransferase; AST = aspartate aminotransferase; BUN = blood urea nitrogen; PT = prothrombin time; PTT = partial thromboplastin time; WBC = white blood cell

Starting from initial tazemetostat exposure, abnormalities in clinical laboratory tests that lead to a change in subject management (eg, dose delay, requirement for additional medication or monitoring) are considered clinically significant and will be recorded on the AE eCRF page. Abnormal laboratory values which are unexpected or not explained by the subject's clinical condition should be repeated until confirmed, explained, or resolved. If laboratory values constitute part of an event that meets criteria defining it as serious, the event (and associated lab values) must be reported as an SAE (see Section 11.2.1).

### 8.3.3 Pregnancy

The effect of tazemetostat on fetal development has not been studied. Consequently, precautions must be taken to avoid any pregnancy that could potentially be conceived during exposure to tazemetostat by EITHER male OR female subjects.

a. Differential should be recorded as absolute counts whenever possible.

## 8.3.3.1. Definition of Childbearing Potential: Female Subjects

A female subject is considered of childbearing potential if she:

- Is anatomically and physiologically capable of becoming pregnant, and
- Will be or could possibly be sexually active with a male while undergoing study treatment with the possibility of posing harm to a fetus

A female subject is considered to be of non-childbearing potential (i.e., physiologically incapable of becoming pregnant) if she:

- Is post-menopausal (at least 12 months consecutive amenorrheic), or
- Is surgically sterilized (i.e., bilateral tubal ligation, total hysterectomy, or bilateral oophorectomy) with surgery at least 1 month before the first dose of study treatment
- Has a documented congenital or acquired disorder that is incompatible with pregnancy

#### 8.3.3.2. Definition of Childbearing Potential: Male Subjects

A male subject is considered of childbearing potential if he:

• Is anatomically and physiologically capable of causing a pregnancy in a female partner

and

• Will be or could possibly be sexually active with a female (who is or may become pregnant) while undergoing study treatment with the possibility of posing harm to a fetus

A male subject is considered to be of non-childbearing potential if he:

• Has a documented successful vasectomy

#### **8.3.3.3.** Pregnancy Testing

All female subjects of childbearing potential must have a negative pregnancy test (urine or serum) at screening and within 21 days of the first dose of study treatment. A separate assessment is required if a negative screening pregnancy test was obtained more than 72 hours before the first dose of study treatment.

Subsequent pregnancy tests should be performed on the first day of every cycle of study treatment and may be either urine or serum.

Positive urine tests are to be confirmed by serum testing.

#### **8.3.3.4. Prevention**

#### 8.3.3.4.1. Female Subjects

Females of childbearing potential must agree to use a highly effective method of contraception, that results in a failure rate of < 1% per year when used consistently and correctly, starting at screening, during study treatment, and for 30 days after the final dose of study treatment, and have a male partner who uses a condom when using hormonal contraceptives.

Acceptable highly effective contraception includes:

- Placement of an intrauterine device
- Established hormonal contraceptive methods: oral, injectable, or implant.

**NOTE:** Female subjects who are using hormonal contraceptives must have been on a stable dose of the same hormonal contraceptive product for at least 4 weeks prior to the first dose of study treatment and must continue to use the same contraceptive during study treatment and for 30 days after discontinuation of study treatment.

Due to the potential of enzyme induction with tazemetostat, female subjects who use hormonal contraceptives should use an additional barrier method of birth control while on study treatment and for 30 days after discontinuation of study treatment.

Female subjects exempt from this requirement are subjects who practice true abstinence when this is in line with the preferred and usual lifestyle of the subject (periodic abstinence [e.g., calendar, ovulation, symptothermal, post-ovulation methods], declaration of abstinence for the duration of the trial, and withdrawal are not acceptable methods of contraception), or have a male partner who is vasectomized. If currently abstinent, the subject must agree to use a highly effective method of contraception as described above if they become sexually active during study treatment, and for 30 days after discontinuation of study treatment.

### **8.3.3.4.2.** Male Subjects

Male subjects of childbearing potential must agree to use condoms with their female partner of childbearing potential prior to enrollment, during study treatment and for 30 days after the final dose of study treatment.

#### 8.3.4 Electrocardiograms (ECGs)

The ECGs will be performed as indicated in the Schedule of Assessments (Table 1). Machine-read ECGs should be reviewed by the investigator at the time of assessment. A single ECG will be recorded unless there is an abnormality, such as prolonged  $QTc(F) \ge 480$  msec, new

arrhythmia, or other clinically significant finding. If such an abnormality is observed, the ECG is to be performed in triplicate at least 2 minutes apart. On days when an ECG reading and a PK blood sample collection are scheduled at the same time, the ECG reading should be performed immediately prior to collection of the PK blood sample, if possible.

ECGs will be read by a Central Reader within 72 business hours and data from the Central Reader should be entered in the clinical database.

#### 8.3.5 Disease Assessment

Disease assessments will be performed as indicated in the Schedule of Assessments and Procedures (Table 1).

Tumor assessments are to be performed by disease-appropriate standard criteria (modified RECIST for thoracic disease or RECIST 1.1 elsewhere) using CT/MRI of known sites of disease as clinically indicated. Bone scan should be performed only if clinically indicated. FDG-PET scan should be performed as clinically indicated at the investigator's discretion, and is not a required tumor assessment.

#### 8.3.6 Pharmacokinetics

The first 12 treated subjects in Part 1 of the study will undergo PK blood sampling. A PK blood sampling scheme will be used in all subsequent subjects enrolled in Part 2 of the study. Blood samples for PK analysis must be drawn per the Schedule of Assessments (Table 1).

A separate Laboratory Manual detailing the PK sample collection, preparation, storage and shipping process will be provided.

#### 8.3.7 Pharmacogenomics (PGx)

A single whole blood sample is to be collected during the screening phase (this sample may be collected on Cycle 1 Day 1 if unable to collect during screening) to provide DNA for analysis of genes involved in drug disposition (i.e., absorption, distribution, metabolism and excretion [ADME]). This will support investigation of whether subject genotype, specifically of ADME genes, is related to the PK of tazemetostat. In addition, DNA sequencing may be performed for determination of germline DNA variants in BAP1.

A separate Laboratory Manual detailing the PGx sample collection, preparation, storage and shipping process will be provided.

#### **8.4.** Correlative Assessments

## 8.4.1 Archive Tumor or Biopsy at Screening

An archival tumor block or biopsy is requested at screening from all subjects enrolled in the study. The diagnostic pathology block or tumor tissue obtained at the time of the subject's initial diagnosis and/or at the time of subsequent procedures is acceptable. The sponsor or its designee will return all blocks to the originating site on completion of the associated analyses. If a tumor block is not available, 10-15 unstained paraffin-embedded tumor tissue containing slides may be provided.

If archive tumor material is not available a tumor biopsy obtained during screening is also acceptable.

Independent central confirmation will **not** be required for study entry (local pathology results showing BAP1-deficiency will be used for study entry). Central confirmation of diagnosis with appropriate IHC will be performed.

Tumor tissue may be analyzed for DNA, mRNA and/or proteins potentially associated for response to tazemetostat up to and including whole genome sequencing.

A Laboratory Manual detailing the tumor sample collection, preparation, storage and shipping process will be provided.

## 8.4.2 Paired Tumor Biopsies to Assess Tazemetostat PD

A pre-dose tumor biopsy (to be collected during screening) and post-dose tumor biopsy for PD analysis is requested from all subjects, when medically feasible, at the first or second tumor assessment (Cycle 3 or 5) or any time between the two assessments. A minimum of 12 patients will be required to provide pre- and post-dose biopsies. If the clinical study accrual has reached 75% and the goals for subjects undergoing tumor biopsy have not been met, only those subjects who can undergo tumor biopsy will be enrolled. If the study subsequently completes accrual of 12 subjects with pre- and post-dose biopsies and the study accrual is still open, the study will then enroll all subjects irrespective of their ability to provide pre- and post-dose biopsies.

A Laboratory Manual detailing the tumor sample collection, preparation, storage and shipping process will be provided.

## 8.4.3 Circulating Tumor DNA

Blood samples are collected at screening and at each response assessment to provide circulating tumor DNA that can be used for identification of candidate biomarkers of response to tazemetostat.

A separate Laboratory Manual detailing the circulating tumor DNA sample collection, preparation, storage and shipping process will be provided.

# 8.4.4 Biomarkers of Response Assessment

Correlations of trends in subjects' clinical response to the molecular characteristics of their tumor (e.g., diagnostic molecular lesions, somatic mutations) may provide evidence of the biological basis for response to tazemetostat. Such investigations are emerging as an effective strategy to inform future clinical development.

#### **8.4.4.1.** Tumor Tissue Sample(s)

Tumor tissue will be assessed to centrally confirm BAP1-deficiency that is required for enrollment. These samples will be used to identify candidate biomarkers of response to tazemetostat via methods, which may include characterization of subjects' tumor heterogeneity using both protein and nucleic acid based methodologies up to and including whole genome sequencing of tumor RNA/DNA. Local pathology results are acceptable for enrollment and eligibility determination.

#### 8.4.5 Assessment of Relapse/Resistance to Tazemetostat

Subjects who initially respond to tazemetostat could subsequently either relapse or become resistant to tazemetostat through as yet unidentified mechanisms such as drug-induced de-novo mutation.

**Tumor Biopsy:** A subsequent tumor biopsy, if medically feasible, at relapse in subjects who achieve a CR or PR to tazemetostat will be requested to enable assessment of adaptive mechanisms of resistance. Tumor characterization by DNA, RNA, or protein may be performed to define molecular changes observed in relapsed tumors.

#### **8.5.** Future Use of Tissue Samples

Not all of the tissue and blood components obtained during this study may be required for the tests that are part of the clinical trial. Following the conclusion of the study, the samples may be used for additional research. These samples will be held for a maximum of 15 years. This research will help to understand disease subtypes, drug response and toxicity, and possibly identify new drug targets or biomarkers that predict subject response to treatment. The use of the

samples for internal research will be done according to the guidelines defined by the FDA guidance for In Vitro Diagnostic Device Studies Using Leftover Human Specimens that are Not Individual Identifiable (issued 25 April 25 2006) and the European Medicines Agency (EMA) Reflection Paper on Pharmacogenetic Samples, Testing and Data Handling (EMEA/CHMP/PGxWP/201914/2006). If a subject requests destruction of their tissue and blood samples and the samples have not yet been de-identified, the sponsor will destroy the samples as described in this FDA guidance. The sponsor will notify the investigator in writing that the samples have been destroyed.

#### 9. CONCOMITANT MEDICATIONS

Documentation of all concomitant medication administered during study treatment will be recorded in the eCRF at each visit.

Because there is a potential for interaction of tazemetostat with other concomitantly administered drugs through the cytochrome P450 system, over-the-counter medications, or alternative therapies must be recorded in the eCRF. The investigator should be alerted if the subject is taking any agent known to affect or with the potential to affect selected CYP450 isoenzymes.

# 9.1. Permitted Medication(s)

- Supportive care measures and symptomatic treatment for any treatment-related toxicity, including short courses of corticosteroids, if clinically indicated
- Prophylactic use of standard anti-emetics
- Intermittent use of dexamethasone is permitted as an antiemetic (not to exceed 0.3 mg/kg/dose dexamethasone or maximum dose of 20 mg) every 12 hours as needed
- Blood and platelet transfusions, as needed per the judgment of the investigator

#### 9.2. Medications to be used with Caution

Substrates of P-gp, CYP3A, CYP2C8, CYP2C9, CYP2C19, and CYP2D6 should be used with caution. Medications that are substrates of CYP3A, CYP2C8, CYP2C9, CYP2C19, or CYP2D6 and have a narrow therapeutic range should be avoided if possible

**NOTE:** A listing of CYP substrates can be found using the following link: http://medicine.iupui.edu/clinpharm/ddis/table.aspx

A list of medications that are CYP3A, CYP2C8, CYP2C9, CYP2C19, and CYP2D6 substrates that have a narrow therapeutic range can be found with following link:

http://www.fda.gov/Drugs/DevelopmentApprovalProcess/DevelopmentResources/DrugInteractionsLabeling/ucm093664.htm

#### 9.3. Prohibited Medication(s)

- Antineoplastic therapy or other investigational therapy for the treatment of cancer
- Prophylactic use of hematopoietic colony stimulating factors

**NOTE:** Therapeutic use of hematopoietic colony stimulating factors is discouraged and should be discussed with the medical monitor and should be conducted according to the 2006 American Society for Clinical Oncology (ASCO) Guideline for use of white blood cell (WBC) growth factors [Smith, 2006].

• Treatment with strong inhibitors or strong inducers of CYP3A4 should not be taken within 14 days prior to first dose of study treatment and for the duration of study.

**NOTE:** A listing of CYP inhibitors, inducers, and substrates can be found using the following link: http://medicine.iupui.edu/clinpharm/ddis/table.aspx

- Enzyme inducing anti-epileptic drug(s) (EIAED) including, but not limited to, carbamazepine, phenobarbital, phenytoin and barbiturates, should not be taken within 14 days prior to the first dose of study treatment and for the duration of study treatment
- All herbal remedies and (including remedies in the form of herbal teas/infusions) are excluded while enrolled in the study
- Medicinal food supplements such as calcium, folic acid, vitamin D, multi-vitamin, etc., which have been taken under the advice from a physician, should be continued at the same dose and regimen during the study provided there are no contraindication as above. These should be listed as concomitant medications in the CRF.
- Any other supplements or alternative therapies should be discussed with the medical monitor prior to enrollment in the study or prior to initiating them during the study.

#### 9.4. Non-Drug Therapies

**Radiation Therapy:** Palliative radiation therapy and potential concurrent dose interruptions will be permitted for pain or severe symptom control after discussion with the medical monitor. Radiation will be limited to non-target lesions only and documented in the eCRF.

Other Palliative Procedures: Other procedures intended for symptom control and potential concurrent dose interruptions may be permitted after discussion with the medical monitor. These procedures will be limited to non-target lesions only and documented in the eCRF.

#### 10. WITHDRAWAL AND REPLACEMENT OF SUBJECTS

## 10.1. Withdrawal of Subjects from Treatment/Procedures

Subjects have the right to withdraw from the study at any time and for any reason without prejudice to future medical care by the physician or institution.

Subjects (or legally authorized representatives) can decline to continue receiving tazemetostat and/or other protocol-required procedures at any time during the study but can continue participation in the study (e.g., for follow-up information). If this occurs the investigator is to discuss with the subject appropriate processes for discontinuation and the options for procedures that may continue such as collection of data, including endpoints and AEs. The investigator must document the agreement in the procedures that the subject will continue with and the level of follow-up that is agreed to by the subject (e.g., in person, by telephone/mail, through family/friends, in correspondence/communication with other physicians, from review of the medical records.)

Reasons for removal from protocol-required treatment or procedures might include the following:

- Disease progression
- Subject request to end study treatment and/or procedures
- Safety concern (e.g., AE, failure to follow contraception or pregnancy, excluded medication required)

# 10.2. Survival Follow-Up

Subjects who permanently discontinue study treatment will be followed (by phone, email or clinic visit) for survival every 12 weeks until death, withdrawal of consent, or lost to follow-up.

Survival follow-up will continue until 80% of treated subjects have died. At such time, the subjects who are continuing on study treatment and have received 12 months of treatment on the current study will be followed and treated on a subsequent extension study.

#### 10.3. Subsequent Therapy After Discontinuation of Study Treatment

Once a subject has permanently discontinued study treatment, every effort should be made to have the subject complete the post-treatment follow-up visit prior to initiating any subsequent anti-cancer therapy (approved or investigational). Post-study anti-cancer therapy will not be provided as part of this study. The subject may receive subsequent anti-cancer therapy at the

discretion of the treating physician. The subsequent anti-cancer therapy should be documented on the eCRF.

## 10.4. Evaluation of Response to Subsequent Anti-Cancer Therapy

To identify a potential epigenetic priming effect of tazemetostat, subjects who are withdrawn from this study due to disease progression and who go on to receive subsequent induction therapy should be followed for response whenever possible. Data to be recorded on the subsequent regimen should include agents received, best response and DOR.

## 10.5. Withdrawal of Subjects from Study

Withdrawal of full consent for a study means that the subjects does not wish to receive further protocol-required treatment, procedures and does not wish to or is unable to continue further study participation. Subject data up to withdrawal of consent will be included in the analysis of the study, and where permitted, publicly available data can be included after withdrawal of consent (e.g., death records). The investigator must document this agreement regarding withdrawal of full consent as well as discuss appropriate procedures for withdrawal from the study.

Reasons for removal of a subject from the study might include the following:

- Death
- Decision by sponsor to terminate the study
- Subject request to withdraw from study
- Lost to follow-up

#### 10.6. Replacement of Subjects

Subjects on Part 2 of the study will not be replaced. Subjects on Part 1 of the study will be replaced if there are not a sufficient number of samples to calculate PK parameters.

#### 10.7. Progression of Disease in Subjects Continuing to Receive Clinical Benefit

There may be some instances when subjects are noted to have modest disease progression. For example, a slight increase in target lesions but with stable non-target lesions, and in the absence of clinical deterioration are receiving continued clinical benefit in the opinion of the investigator. In such a situation, the investigator should contact the medical monitor to discuss the assessment of risk: benefit of keeping the subject on study.

Prior to declaring progressive disease, the investigator should be certain that special circumstances on progression defined by RECIST 1.1 are not met. In these situations of equivocal findings of progression, subjects may continue treatment until the next scheduled disease assessment. If progression is confirmed, the date of the previous assessment will be used as the date of disease progression.

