  - **PK Part 2:** The subjects in Part 2 will have 2-mL blood samples for PK analysis collected at the following time points: Cycle 1 Day 1: pre-dose, and 1, 3, and 6 hours post-dose; Cycle 1 Day 15: pre-dose, 1, 3, and 6 hours post-dose; Day 1 of Cycles 2 through Cycle 4: pre-dose. All PK blood samples may be drawn from either a central venous catheter or a peripherally placed intravenous catheter. Exact time of draw must be recorded.
- 1. **Tumor Tissue:** Archival tissue (block or 10-15 slides) will be requested for central confirmation of pathology, IHC, and additional molecular testing, e.g., detection of somatic mutations and/or candidate biomarkers of response. If archived tumor material is not available, tumor biopsy obtained during screening is acceptable.
- m. **Tumor Biopsy for Tazemetostat PD:** A minimum of 12 subjects will be required to provide pre-dose (to be collected at screening) and post-dose biopsies (formalin-fixed paraffin-embedded [FFPE] blocks) to assess H3K27me3 starting at or following the first or second tumor assessments (Cycle 3 or 5). If the clinical study accrual has reached 75% and the goals for subjects undergoing tumor biopsy have not been met, only those subjects who can undergo tumor biopsy will be enrolled. If the study subsequently completes accrual of 12 subjects with pre- and post-dose biopsies and the study accrual is still open, the study will then enroll all subjects irrespective of their ability to provide pre- and post-dose biopsies.
- n. **Tumor Biopsy at Disease Progression:** An FFPE tumor biopsy is requested, where medically feasible, at disease progression in subjects who achieve a PR or better to tazemetostat.
- o. **Tumor Assessment:** Tumor assessments by disease-appropriate standard criteria (modified RECIST for thoracic disease or RECIST 1.1 elsewhere) using CT/MRI of known sites of disease as clinically indicated. Bone scan should be performed only if clinically indicated. Tumor assessments must be performed at screening and every 6 weeks (±3 days) or sooner, if clinically indicated, from start of treatment. FDG-PET scan should be performed as clinically indicated at the investigator's discretion, and is not a required tumor assessment.
- p. Disease Assessment and Survival Status: Survival follow-up will be conducted approximately every 12 weeks on all subjects, unless the subject withdraws consent.

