### 13.3.2 Interim Analyses

If, in consultation with the investigators, the PK and safety profiles of tazemetostat in Part 1 are acceptable, then the 400 mg tablets will be used in Part 2.

For Part 2, the decision rules at the end of Stage 1 are listed in the table below.

	Part 2 (Relapsed/Refractory Synovial Sarcoma)
Null Hypothesis	CR+PR+SD at Week 12 ≤20%
Alternative Hypothesis	CR+PR+SD at Week 12 ≥35%
Stage 1 Sample Size (n1)	30
Stage 1 Rejection of Study Treatment (r1)	4

The end of Stage 1 occurs when the first 30 treated subjects have completed at least the Week 12 assessment, completed the final study visit or terminated early from the study, whichever is sooner.

- At the end of Stage 1, if there are ≤ 4 CR + PR + SD out of 30 subjects, then reject the new treatment and terminate the study for futility. When there are ≥5 CR + PR + SD out of 30 subjects, the study continues to Stage 2.
- At the end of the study, if there are ≤16 CR + PR +SD out of 55 treated subjects, then reject the new treatment. When there are ≥17 or more CR + PR +SD out of 55 subjects, then the new treatment is accepted.

The interim analysis planned at the end of Stage 1 may occur sooner if the Stage 1 rejection criterion is surpassed before all 30 subjects are treated and followed 12 weeks. In this scenario, the total sample size (Stage 1 + Stage 2) would still remain unchanged at 55 subjects.

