# 13.4. Efficacy Analyses

### 13.4.1 Analysis of Primary Endpoint

The data cut-off for the Week 12 analysis at the end of the study will occur after all treated subjects have completed at least the Week 12 assessment; completed the final study visit; or terminated early from the study. The DCR at Week 12 is defined as the percentage of subjects with a response of CR, PR or SD at the Week 12 assessment, as per modified RECIST [Nowak, 2005] for thoracic disease or RECIST 1.1 elsewhere.

Subjects with non-evaluable or missing response will be treated as not having disease controlled; i.e., they will be included in the denominator when calculating the DCR. As a specific example, subjects with disease progression or death prior to the Week 12 assessment will be included in the denominator. In addition to the DCR at Week 12, an exact 90% CI for this rate will be provided.

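### Does back-dating of confirmed progression let subjects with progression at Week 12 count as disease control?

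*Combined protocol and SAP*

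**What the plan says.** Section 10.7 deals with progression that is not clear-cut: "In these situations of equivocal findings of progression, subjects may continue treatment until the next scheduled disease assessment". It then fixes the date: "If progression is confirmed, the date of the previous assessment will be used as the date of disease progression". Footnote o to Table 1 sets the scan interval: "Tumor assessments must be performed at screening and every 6 weeks (±3 days) or sooner, if clinically indicated, from start of treatment". The next scheduled scan after Week 12 is therefore at about Week 18, though an earlier one is allowed.

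For the primary analysis of Part 2, section 13.4.1 says: "The DCR at Week 12 is defined as the percentage of subjects with a response of CR, PR or SD at the Week 12 assessment". It also says: "Subjects with non-evaluable or missing response will be treated as not having disease controlled". Its worked example mentions progression or death before the Week 12 assessment and is silent on progression later dated to that assessment. The final cut-off "will occur after all treated subjects have completed at least the Week 12 assessment", or has finished or left the study. Section 13.3.2 times the interim look in the same way: "The end of Stage 1 occurs when the first 30 treated subjects have completed at least the Week 12 assessment".

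The decision rules (sections 13.1 and 13.3.2) stop the study at 4 or fewer controlled of 30 and accept the drug at 17 or more of 55. The null rate is 20% and the alternative 35%. Section 13.3.3 leaves complete analysis details to the SAP.

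**The concern.** The resolving scan comes about six weeks after the scan on which the endpoint is read, and no sentence joins the two rules. The investigator calls response in an open-label study. A subject kept on treatment under section 10.7 looks most like stable disease, because section 7.4 requires treatment to stop at progression. If stable disease is entered and never revisited, one subject can be a success in DCR and a Week 12 event in PFS, and PFS at 12 weeks is a named secondary endpoint.

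The final decision turns on one subject, 16 against 17 of 55. If progressed subjects were counted as controlled, the false-positive rate would rise and the futility stop would weaken.

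**Working it through.** **Inputs.** From sections 13.1 and 13.2.1: first stage 30 subjects, stop at 4 or fewer; total 55, accept at 17 or more; null rate 0.20; alternative 0.35; one-sided alpha 0.05.

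**The plan's own figures.** Probability of early stopping = P(X ≤ 4), X ~ Bin(30, p).
- p = 0.20: 0.2552 (stated 0.255).
- p = 0.35: 0.0075 (stated 0.008).

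Both reproduce.

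**Acceptance probability.** Sum over x = 5 to 30 of P(X₁ = x) × P(X₂ ≥ 17 − x), with X₁ ~ Bin(30, p) and X₂ ~ Bin(25, p). At p = 0.20 this is 0.0367, so the design has some room below 0.05.

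**Case A: every subject exposed, none ever re-scored.** Assume a true rate of 20% after back-dating, and that 1 or 2 of 55 subjects are wrongly counted. Then 1/55 = 1.8 points and 2/55 = 3.6 points.

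| Apparent rate | Acceptance | Stage 1 stopping |
|---|---|---|
| 0.200 | 0.0367 | 0.255 |
| 0.218 | 0.074 | 0.186 |
| 0.236 | 0.133 | 0.131 |

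Adding exactly one or two subjects to the final count, instead of shifting the rate, gives 0.069 or 0.120.

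**Case B: confirmed cases are scored as not controlled once the next scan is in.** Both cut-offs are set for the study as a whole. The final one waits until every treated subject has at least Week 12 data, so subjects enrolled earlier will usually have passed Week 18. Only those whose Week 12 scan falls within about six weeks of the cut-off are unresolved. Let the last k of the 25 second-stage subjects have rate 0.20 + q and everyone else 0.20.

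| k | q = 0.018 | q = 0.036 | q = 0.05 | q = 0.10 |
|---|---|---|---|---|
| 5 | 0.039 | 0.042 | 0.044 | 0.053 |
| 10 | 0.042 | 0.048 | 0.053 | 0.074 |

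At the rates used in Case A, acceptance stays below 0.05. It passes 0.05 only at higher per-subject rates, for which the documents offer no support either way.

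**Stage 1.** If the last 5 of the first 30 are exposed at 1.8 or 3.6 points, stopping under the null is about 0.24 or 0.23, against 0.255. Passing the futility look does not by itself accept the drug. A single-stage rule of 17 of 55 has type I error 0.0367, the same to four decimals as the two-stage rule. An error at Stage 1 that is corrected by the final analysis therefore adds almost nothing to false acceptance.

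**The texts side by side.** Section 10.7 supplies a progression date. Section 13.4.1 needs a response category. An equivocal Week 12 scan could be entered as stable disease (controlled), as progression (not controlled) or as non-evaluable (not controlled under section 13.4.1). The documents do not choose among these.

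**The case for a change.** The strongest reply is that the scoring gap touches all 55 subjects, since a Week 18 scan helps only if some rule says to use it. Stable disease is also the natural entry for a readable scan in a subject kept on treatment; non-evaluable fits less well. In addition, section 13.3.2 lets the interim look happen early once the Stage 1 criterion is surpassed, so a fifth apparent success could open Stage 2 while its scan is unresolved. A 1-point rise in the apparent rate across all subjects already gives 0.055.

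Part of this stands: no sentence states the convention, and the two endpoints could disagree for the same subject. The rest is weaker.
- Leaving a subject as controlled means ignoring a progression date of Week 12 that the protocol itself has assigned.
- Section 13.1 states the null in terms of response at the Week 12 tumor assessment. Against that hypothesis as written, type I error is 0.0367 whatever later scans show; the inflation appears only when the back-dated rate is put in its place.
- The bias need not run one way, because non-evaluable entries push DCR down.
- Section 4.2 deliberately accepts unconfirmed responses at the interim for timeliness and does not halt enrollment for it, and section 14 has the independent data monitoring committee review futility.

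The obvious remedies have costs too. Counting every unresolved equivocal scan as a failure would misclassify subjects whose progression is not confirmed. Waiting for the next scan could delay a cut-off by up to about six weeks.

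**Conclusion.** No change to the plan follows. This is an unwritten scoring convention: the documents permit a subject to be controlled in DCR and progressed at Week 12 in PFS, but they do not require it. The sensible reading, that progression dated to Week 12 is not disease control at Week 12, removes the discrepancy for every subject whose next scan is available at the cut-off.

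On that reading, and assuming 5 to 10 unresolved subjects with an added 1.8 to 3.6 point chance each, the false-positive probability is 3.9% to 4.8%, against 3.7% for the design and a 5% limit. The figures of 7.4% and 13.3% are correct arithmetic but assume that no case is ever re-scored. The number of unresolved subjects and the frequency of equivocal scans are assumptions; at 10% per subject with 10 exposed, the probability would be 7.4%. The separate SAP to which section 13.3.3 defers is not among the documents reviewed, so it cannot be said that the convention is missing from the final analysis plan.
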